APPENDIX 3: Subjective Ocular Tolerability and Discomfort Assessment

Subjects will be asked to grade ocular tolerability and discomfort in both eyes at all study visits.

Subjective Ocular Discomfort Grading

Subjects will assess discomfort using the following subjective scale ([Maca et al. 2010](#)). This parameter will consist of questioning about superficial pain, foreign body, or gritty sensation, itching, burning, and other forms of non-specific discomfort.

- Grade 0: Absent
- Grade 0.5: Very mild
- Grade 1: Mild
- Grade 2: Moderate
- Grade 3: Severe
- Grade 4: Intolerable

Subjective Tolerability Using a Visual Analog Scale for Pain

Subjects will assess tolerability using the following subjective visual analog scale ([Scoville et al. 1985](#)). A visual analogue scale is performed by asking subjects to indicate on an unmarked 100-mm line the intensity of their pain. A mark of “0” represents no sensation while “100” indicates the worst imaginable pain. The location of the mark on the line is then measured with a ruler (in mm) to provide a numeric score.

Self-Evaluation Form	
Participant No.	Patient's Initials:
Injection date: _____	
Today's date/time: _____	
Left Eye extremely irritated	Right Eye extremely irritated
not irritated	not irritated
Which eye feels more uncomfortable? (circle one)	
left	right
no difference	

APPENDIX 4: Common Terminology Criteria for Adverse Events (CTCAE)
Version 5.0

Adapted from:

https://ctep.cancer.gov/protocolDevelopment/electronic_applications/docs/CTCAE_v5_Quick_Reference_5x7.pdf

APPENDIX 5: Summary of Changes

The following changes were made to Protocol EYP-2102-001 as Amendment 3 (v2.0):

Section(s)	Description of Change / Rationale
Synopsis Section 3.1 , Overall Study Design Figure 3-1 , Study Design Schema, Study EYP-2102-001 Section 5.1 , Measurements and Evaluations by Visit	
Added details to state that the Sponsor has decided to stop subject enrollment and will continue to monitor subjects randomized to Yutiq 0.05 mg.Enrollment has been stopped due to reasons other than safety or efficacy, following FDA advice received on January 24, 2022. The Sponsor is reevaluating the development program of Yutiq 0.05 mg.Updated these sections to describe the modified protocol schedule for those subjects randomized to Yutiq 0.05 mg.Added the information that subjects who were randomized to sham injection will be discontinued from the study and will undergo their EOS visit.
Section 3.2 , Discussion of Study Design, Including the Choice of Control Groups	
Clarified the masked versus unmasked personnel requirements that were included in Administrative Letter #2 (dated January 3, 2022).
Section 3.3 , Duration of Study	
Clarified the modified protocol scheduled
Section 4 , Selection and Withdrawal of Subjects	
Added text to state that subject enrollment has been stopped.
Synopsis Section 4.1 , Inclusion Criteria #3	
Clarified the inclusion criteria #3 that was included in Administrative Amendment 3 (March 1, 2022).
Synopsis Section 4.1 , Inclusion Criteria #19	
Added the marketed uveitis treatment XIPERE™ that was included in Administrative Amendment 3 (March 1, 2022).
Section 5.1 , Measurements and Evaluations by Visit Table 5-1 , Schedule of Study Procedures and Assessments, Study EYP-2102-001	
Removed Month 9 to align with modified protocol schedule for the subjects were treated with Yutiq 0.05 mg.
Table 5-1 , Schedule of Study Procedures and Assessments, Study EYP-2102-001 (footnote “c”). Section 8.4 , Clinical Laboratory Evaluations	
Added “Screening only” for the tuberculosis testing. Tuberculosis testing will not be performed at the final visit.
Section 6.2.1 , Yutiq 0.05 mg Injection Procedure	
Clarified the timing for biomicroscopy post-injection that was provided in the Administrative Letter #2 (dated January 3, 2022).
Section 11.1 , Determination of Sample Size	
Added text that the Sponsor has stopped enrollment of the study.

Section(s)	Description of Change / Rationale
Appendix 2 , Slit Lamp Biomicroscopy, Ophthalmoscopy, and Intraocular Pressure	
Clarified the requirement for dilation for the slit lamp examination assessment that was included in the Administrative Letter #3 dated March 1, 2022.
Appendix 5 Summary of Changes	
Added Appendix 5 due to Amendment 3 changes.
Global protocol changes	
Miscellaneous typographical and formatting issues were corrected, and some hyperlinks were fixed and/or added.

6.1.	Appendix 1: List of Abbreviations.....	22
6.2.	Appendix 2: Supporting Study Information.....	23
6.2.1.	Disposition of Subjects.....	23
6.2.2.	Demographics.....	23
6.2.3.	Baseline and Disease Characteristics	23
6.2.4.	Protocol Deviations	23
6.2.5.	Medical History and Concurrent Illnesses	23
6.2.6.	Prior/Concomitant Medications	23
6.3.	Appendix 3: Data Handling Conventions	25
6.3.1.	Missing Date Imputation	25
7.	References	27

Version History

SAP Version	Date	Change	Rationale
1.0	08MAY2023	Not applicable	Original version

1. Introduction

This document presents the statistical analysis plan (SAP) for the protocol EYP-2102-001, a phase 3, multicenter, prospective, randomized, masked, controlled, safety and efficacy study of fluocinolone acetonide (FA) intravitreal 0.05 mg insert (Yutiq 0.05 mg) in subjects with chronic non-infectious uveitis affecting the posterior segment of the eye.

This SAP was developed in accordance with ICH E9 guideline. This SAP is to provide details of the statistical analyses based on the protocol version 3.0, dated July 20, 2022. The SAP will be finalized prior to database lock. Any deviations from the SAP after database lock and reasons for such deviations will be described and documented in the clinical study report.

The Sponsor decided to stop enrollment in early May 2022. Subjects who were randomized to Yutiq 0.05 mg will continue to be monitored on a modified-protocol schedule. The subjects who had been treated with sham injection were discontinued from the study. Consider the fact that the study was terminated early, the analyses described in this SAP has been limited to the scope per the interest of EyePoint Pharmaceuticals, Inc. For such a reason, the list of endpoints and analyses in this SAP is a reduced list from the study protocol.

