Eligibility determination, informed consent, demographics, medical and ophthalmic history (including a detailed history of the management of their uveitis over the previous 52 weeks), vital signs, clinical laboratory testing, ophthalmic examinations (includes BCVA, IOP, dilated ophthalmoscopy, and anterior, posterior and intermediate slit lamp examination), subjective ocular tolerability and discomfort assessment, concomitant medications, and pregnancy testing as appropriate.

Treatment Day (Day 1):

Eligibility confirmation including meeting the entry criteria for anterior chamber cells, vitreous haze, IOP, and visual acuity on Study Day 1, and then randomization to either intravitreal Yutiq 0.05 mg or sham injection. Following determination of study eye, subjects will receive either Yutiq 0.05 mg or the sham injection. Assessments on that day will include vital signs, ophthalmic examinations, spectral-domain – optical coherence tomography (SD-OCT), subjective ocular tolerability and discomfort assessment, pregnancy test if appropriate, concomitant medications, and adverse events (AEs).

Follow-up Visits:

Following injection on Study Day 1, subjects who were treated with Yutiq 0.05 mg will return for study visits on Days 7, 28, and at Months 2, 3, 6, and 12. Evaluations on these days will include: review of concomitant medications, vital signs, ophthalmic examinations, IOP, SD-OCT, subjective ocular tolerability and discomfort assessment, and AEs. All subjects treated with Yutiq 0.05 mg in the study will be followed for 52 weeks. In early May 2022, those subjects who had been treated with sham injection were discontinued from the study. Sham-treated subjects subsequently had their End of Study (EOS) evaluation.

Masking: Study subjects will receive either Yutiq 0.05 mg or a sham injection. Subjects and study staff conducting clinical study assessments, except for the clinician performing the injection procedure, will be masked to randomized treatment assignment.

Concomitant Medications:

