3 INVESTIGATIONAL PLAN

3.1 Overall Study Design

[figure not shown]
The protocol was originally planned to be a 52-week, prospective, randomized, masked (subject and outcome assessor), controlled, safety and efficacy study of intravitreal Yutiq 0.05 mg compared to sham injection with a primary efficacy and safety readout at 24 weeks.

The Sponsor has decided to stop enrollment for reasons other than safety or efficacy in early May 2022, following FDA advice received on January 24, 2022. The Sponsor is reevaluating the development program of Yutiq 0.05 mg. Subject enrollment has been stopped, and all subjects have been unmasked. Subjects who were randomized to the sham injection were discontinued from the study and underwent their EOS visit. Subjects who were randomized to sham injection may have been treated with standard of care medication, if necessary. Subjects who were randomized to Yutiq 0.05 mg will be followed on a modified protocol schedule through Month 12 (or ET) and evaluated for efficacy and safety.

As depicted in [Figure 3-1](#), subjects will receive either Yutiq 0.05 mg or a sham injection on Day 1 of the study. Subjects who were treated with Yutiq 0.05 mg will be assessed over the following 52 weeks on a modified protocol schedule according to the schedule presented in

Table 5–1. Subjects who were randomized to the sham injection were discontinued from the study and underwent their EOS visit.

Figure 3-1: Study Design Schema, Study EYP-2102-001

Note: The sponsor decided to stop enrollment for reasons other than safety or efficacy in early May 2022, following FDA advice received on January 24, 2022. The Sponsor is reevaluating the development program of Yutiq 0.05 mg. Subject enrollment in the study has been stopped. All subjects who were currently enrolled have been unmasked. Subjects who were to receive Yutiq 0.05 mg will be followed on a modified protocol schedule through Month 12 (or ET).

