10.2 Secondary Efficacy Endpoints

The secondary efficacy endpoints will include:

- Proportion of subjects who have a recurrence of uveitis in the study eye within 52 weeks
- Proportion of subjects who have a recurrence of uveitis in the fellow eye within 24 and 52 weeks
- Mean change from baseline in BCVA letter score in the study eye at 24 and 52 weeks
- Number of recurrences of uveitis within 24 and 52 weeks
- Time to recurrence of uveitis through 24 and 52 weeks
- Number of adjunctive treatments required to treat recurrences of uveitis at 24 and 52 weeks
- Proportion of subjects with recurrence of iridocyclitis defined as a >2 -step increase in anterior chamber cells per HPF (1.6 \times using a 1-mm beam) in the study eye compared to baseline at 24 and 52 weeks.
- Proportion of subjects with resolution of macular edema as measured by SD-OCT imaging at Day 28 and at Months 2, 3, 6, and 12.

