4.2. Primary Efficacy Endpoint Analysis

4.2.1. Definition of Endpoint

The primary efficacy endpoint is the proportion of subjects who have a recurrence of uveitis in the study eye within 24 weeks (6 months) after receiving study treatment. Recurrence is defined as:

- An increase in the vitreous haze of ≥ 2 steps compared to baseline at the Week 24 visit, or any visit time point prior to the Week 24 visit after the Study Day 7 visit

Or

- A deterioration in visual acuity of at least 15 letters BCVA compared to baseline at the Week 24 visit, or any visit time point prior to the Week 24 visit after the Study Day 7 visit.

Any criterion used to define recurrence must be attributable only to noninfectious uveitis. To prevent post-procedural inflammatory reactions from being reported as uveitis recurrences, assessments for recurrence of uveitis begin after the Study Day 7 visit.

The study protocol stated to impute subjects who don't complete Week 24 eye examinations and subjects who take prohibited medications as having a recurrence. Consider the fact that the study was terminated early, no imputation will be implemented. Summary of the primary efficacy endpoint will be based only on the observed data from the subjects who reached Week 24.

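### Written after unmasking, the SAP drops time to recurrence and three other secondary endpoints without listing them in 4.8, leaving no recurrence endpoint that accounts for the shortened sham follow-up

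*SAP*

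**What the plan says.** Protocol 10.2 lists eight secondary efficacy endpoints, among them "Time to recurrence of uveitis through 24 and 52 weeks". SAP 1.1 and 4.3.1 keep four. The SAP Introduction points to the early termination, says that "the analyses described in this SAP has been limited to the scope per the interest of" the sponsor, and concludes that "the list of endpoints and analyses in this SAP is a reduced list from the study protocol". No reason is given for any single endpoint. SAP 4.8, the section for departures from the protocol's analyses, has two entries (no hypothesis test, and the analysis populations). The dropped endpoints are not there.

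On follow-up, Protocol 3.1 reports: "Subject enrollment has been stopped, and all subjects have been unmasked". The protocol synopsis adds: "In early May 2022, those subjects who had been treated with sham injection were discontinued from the study". Treated subjects are followed to Month 12.

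On recurrence, SAP 4.2.1 removes the protocol's imputation rules and makes the primary summary "based only on the observed data from the subjects who reached Week 24". SAP 4.3.1.1 and 4.3.2 apply the same assessment and method to the 52-week proportion. SAP 4.3.1.3 counts recurrences within 24 and 52 weeks and names no denominator.

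**The concern.** Two things come together. The list of endpoints was cut when treatment assignments were known, and the section meant to record such changes is silent on it. A reader of the study report therefore cannot tell why these four endpoints went and the other four stayed.

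The cut also removes the one listed recurrence endpoint built for incomplete follow-up, in a trial where the sponsor ended follow-up early in the sham arm only. Time to recurrence would use every sham subject up to the last examination. Under the retained definitions, a recurrence that was actually seen in a sham subject before the stop can vanish from the recurrence results.

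**Working it through.** **1. Endpoints side by side** (Protocol 10.2 against SAP 1.1 and 4.3.1)

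| Protocol secondary endpoint | In the SAP list? | What remains elsewhere in the SAP |
|---|---|---|
| Study-eye recurrence, 52 weeks | Yes | |
| Fellow-eye recurrence | No | Abnormal fellow-eye haze by arm and visit (4.2.2) |
| BCVA change | Yes | |
| Number of recurrences | Yes | |
| Time to recurrence | No | Nothing |
| Number of adjunctive treatments | No | Proportion receiving rescue, not the number of treatments (4.4.7.1) |
| Iridocyclitis recurrence (>2 steps) | No | Anterior chamber cell increase of ≥2 steps, a different threshold (4.4.5.1) |
| Macular edema resolution | Yes | |

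Eight in the protocol, four kept, four dropped.

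**2. Timing.** No unmasking date is given. The SAP is based on "protocol version 3.0, dated July 20, 2022", and the protocol text already reports unmasking in the past tense. I take the supplied protocol to be that version. Its Appendix 5 labels the amendment v2.0; if the text is older than v3.0, the unmasking is no later than assumed here. From 20 July 2022 to 8 May 2023 is 292 days (9.6 months). From 1–10 May 2022 it is 372–363 days (about 12 months). Hence about 10 to 12 months.

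**3. What happens to a sham subject who recurs at Day 28 and is stopped at Month 3**

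- Primary proportion: the subject did not reach Week 24, so is left out of numerator and denominator.
- 52-week proportion: left out under the same method. The completer restriction is written out only for the primary; carrying it over is the natural reading of 4.3.1.1 and 4.3.2. A sham subject needed Day 1 by about May 2021 to reach Week 52.
- Number of recurrences: may be counted, but with no adjustment for shorter observation.
- Time to recurrence (dropped): would count as an event at Day 28.

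**4. Size.** The plan has no figure to reproduce: actual sham numbers, enrolment dates and sham follow-up are not stated. To reach 168 days by 1–10 May 2022, a sham subject needed Day 1 by 14–23 November 2021. If Month 6 is taken at the early edge of its ±28-day window (Day 140), the date is 12–21 December 2021.

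Assume uniform accrual over L days up to the stop, no other dropout, and T = 168.

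- Share reaching Day T = 1 − T/L.
- Sham person-time to Day T is proportional to T(L − T/2) = 168(L − 84).
- Person-time of those not reaching T is proportional to T²/2 = 14,112.
- Discarded share = T/(2L − T), or 100% if L ≤ T.
- If Day 140 is enough, the excluded person-time is 140²/2 = 9,800, over the same total.

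| Accrual (30.44 days per month) | Reach Day 168 | Person-time discarded | Reach Day 140 | Person-time discarded |
|---|---|---|---|---|
| 4 months (121.8 d) | 0% | 100% | 0% | 100% |
| 6 months (182.6 d) | 8% | 168/197.3 = 85% | 23% | 9,800/16,572 = 59% |
| 9 months (274.0 d) | 39% | 168/379.9 = 44% | 49% | 9,800/31,913 = 31% |
| 12 months (365.3 d) | 54% | 168/562.6 = 30% | 62% | 9,800/47,255 = 21% |

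More than half is discarded if L < 1.5 × 168 = 252 days (36 weeks) on the strict rule. With the window, the limit is L < 84 + 9,800/84 = 201 days (about 29 weeks).

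**The case against.** The case for leaving the SAP alone is substantial. Protocol 11 lets the SAP modify planned analyses and requires an amendment only for major changes to the primary endpoint or its analysis. The Introduction says openly that the list was cut. SAP 4.1.1 rules out hypothesis tests and promises by-subject listings, so nothing is hidden and no inference rests on the missing endpoints. Three of the four dropped endpoints survive in part. A stop on a calendar date for reasons other than safety or efficacy acts as administrative censoring, so a completer proportion mainly loses information and need not be biased. A time-to-event display also has a flaw of its own: sham subjects had an extra end-of-study examination around May 2022, while treated subjects had no matching scheduled visit between Month 3 and Month 6. Recurrences picked up only there would count against sham.

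All of this stands, and it limits the point to documentation and description. It does not remove it. Listings are not a summary by arm, general disclosure is not a reason per endpoint, and finalising before database lock protects little once assignments are known. The examination imbalance is a reason to show the curve two ways.

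Three stronger readings are tempting and not supported:

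- A reader might infer that endpoints were chosen by their results. The documents do not show that. They only lack the record that would exclude it.
- A reader might infer that most sham information is lost. That depends on an accrual length the documents do not give, and at 9 or 12 months it is false by person-time.
- A reader might infer that nothing else uses the early sham visits. By-visit haze and BCVA with their threshold changes (SAP 4.2.2) and macular edema from Day 28 (SAP 4.3.1.4) do. They are not recurrence endpoints and do not follow a subject to a first event.

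**Conclusion.** The point holds for documentation and for recurrence. Half of the protocol's secondary endpoints were removed after unmasking without individual reasons and without an entry in SAP 4.8. With time to recurrence gone, every retained recurrence endpoint either excludes sham subjects stopped early or counts events without regard to unequal observation. The raw count would tend to understate sham recurrences.

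The size cannot be fixed from the documents. On assumed uniform accrual of 6 to 12 months, 85% down to 30% of sham person-time to a strict Week 24 drops out of the primary proportion, or 59% down to 21% if the early edge of the Month 6 window counts. The change is worth making because the endpoint is already in the protocol and the data exist. It would not turn a stopped, descriptive study into a comparative one.

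**What to change.** Restore time to first recurrence as a descriptive Kaplan-Meier summary by arm, with numbers at risk. The event is the first qualifying examination after Day 7, with censoring at the last examination. Show it:

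- with both arms cut at the sham discontinuation date, and with full follow-up;
- with and without recurrences found only at the sham end-of-study examination. In the version without, end every sham subject's follow-up at the last scheduled visit before that examination, so that time at risk goes out together with the events.

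In SAP 4.8, list each of the four dropped endpoints with its own reason, and state that the reduction was made after unmasking.

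Cost: one figure, one table and a short paragraph, from data already collected (Protocol 7.6 has each recurrence and its treatment recorded in the eCRF). Downside: a descriptive curve in a small sample, which supports no formal inference and should be labelled so.

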1.1. Objectives and Endpoints

Objectives	Endpoints
Primary	Primary Efficacy Endpoint The proportion of subjects who have a recurrence of uveitis in the study eye within 24 weeks (6 months) after receiving study treatment
Secondary	Secondary Efficacy Endpoints 
• Proportion of subjects who have a recurrence of uveitis in the study eye within 52 weeks• Mean change from baseline in best corrected visual acuity (BCVA) letter score in the study eye at 24 and 52 weeks• Number of recurrences of uveitis within 24 and 52 weeks• Proportion of subjects with resolution of macular edema as measured by Spectral-domain Optical Coherence Tomography (SD-OCT) imaging at Day 28 and at Months 2, 3, 6, 9, and 12.
Safety	

	
• Systemic Adverse Events (AEs)• Ocular AEs, including IOP elevation• Medications/procedures required to control elevated IOP• Development or worsening of cataract• Cataract-related procedures• Clinically significant ocular changes• Procedure related AEs• Subjective ocular tolerability and discomfort assessments• Vital signs• Clinical laboratory assessments• Use of rescue and concomitant medications
--	--

1.2. Study Design

The protocol was originally planned to be a 52-week, prospective, randomized, masked (subject and outcome assessor), controlled, safety and efficacy study of intravitreal Yutiq 0.05 mg compared to sham injection with a primary efficacy and safety readout at 24 weeks. A total of approximately 60 subjects (30 subjects in the Yutiq 0.05 mg group and 30 in the sham treatment group) were to be enrolled at approximately 40 sites in the US. One eye in each subject will be designated as the study eye.

The Sponsor decided to stop enrollment in early May 2022 for reasons other than safety or efficacy, following FDA advice received on January 24, 2022. Subjects who were randomized to Yutiq 0.05 mg will continue to be monitored on a modified-protocol schedule through Month 12 (or ET) and evaluated for efficacy and safety. Those subjects who had been treated with sham injection were discontinued from the study and subsequently had their End of Study (EOS) evaluation.

[figure not shown]
Subjects will receive either Yutiq 0.05 mg or a sham injection on Day 1 of the study on the study eye and will be assessed over the following 52 weeks according to the schedule of study procedures and assessment.

Yutiq 0.05 mg is a non-erodible intravitreal implant in a drug delivery system that contains 0.05 mg of FA and is designed to release FA at a rate of 0.25 µg/day into the vitreous humor for at least 6 months. Yutiq 0.05 mg is preloaded into a single-dose applicator to facilitate injection of the implant directly into the vitreous.

To ensure the health of both eyes, observations of both the study eye and non-study (fellow) eye

should be made at all visits as described in the schedule of study procedures and assessments. Ocular data will be collected for both eyes at all visits except for the SD-OCT assessments.

Figure 1. Study Design Schema

